1.2.6 Clinical experience in humans

The safety, tolerability, pharmacokinetics and exploratory pharmacodynamics of BI 443651 have been investigated in a randomised, single-blind and placebo-controlled trial in healthy male subjects, study 1363.1 [[c02861250-03](#)]. The First-into-Man (FIM) study is complete with single inhaled doses of 10, 30, 100, 300, 900, 1800, 2700, 3600 µg or their matching placebo administered to 63 healthy male volunteers. Details are provided below for both PK and safety.

Summary of PK data from SRD trial (study 1363.1)

Boehringer Ingelheim

BI Trial No.: 1363.7

c11830963-01

Trial Protocol

23 February 2017

Page 24 of 94

Proprietary confidential information © 2017 Boehringer Ingelheim International GmbH or one or more of its affiliated companies

Proprietary confidential information © 2017 Boehringer Ingelheim International GmbH or one or more of its affiliated companies

Table 1.2.6:1

Pharmacokinetic parameters and geometric mean (gCV %) of BI 443651 following a single dose administration of 10 to 3600 µg BI 443651 in healthy male subjects in study 1363.1

Summary of clinical safety data from SRD trial (study 1363.1)

Safety, tolerability and pharmacokinetics of BI 443651 have been investigated in a partially randomised (within dose groups), single-blind, placebo-controlled trial (study 1363.1). This First-into-Man study included single inhaled doses of 10, 30, 100, 300, 900, 1800, 2700 and 3600 µg or placebo administered via the Respimat device to 63 healthy male volunteers (47 on BI 443651).

Adverse events were reported by 16 of 47 subjects (34.0 %) following treatment with BI 443651 and 4 of 16 subjects (25.0 %) following treatment with placebo.

Ten of 47 subjects (21.3%) experienced AEs that were regarded by the investigator as possibly related to the administration of study drug, all from the BI 443651 treatment groups. These include cough (7 subjects), throat irritation (2 subjects), dysphoria (1 subject) and headache (1 subject).

All AEs were of mild or moderate intensity and recovered or were sufficiently characterized by follow-up. There were no severe nor serious AEs reported. The most frequently reported AE was headache, observed in 7 of 47 subjects (14.9%) after BI 443651 treatment without dose ordering. One subject reported headache in the placebo group (6.3%).

Cough was reported in 7 subjects (14.9%) receiving BI 443651 in a dose ordered fashion: 1 subject at 1800 µg, 3 subjects at 2700 µg and 3 subjects at 3600 µg. No subjects receiving placebo reported cough.

Throat irritation was reported by 3 subjects (6.4%) receiving 1800, 2700 and 3600 µg (1 subject in each dose group) of BI 443651, while none in the placebo group. With respect to the type, incidence and severity of AEs other than described above, there was no notable difference between the dose levels.

In summary, clinical safety data of trial 1363.1 showed that single doses of up 3600 µg BI 443651 were well tolerated. A bitter taste was noted by all volunteers administered the highest concentration (300 µg/inhalation), but not in the corresponding placebo group. A reversible drop in FEV₁ and FVC was observed in some volunteers. No clinically relevant abnormalities were observed in ECG recordings, vital sign or safety laboratories. Adverse events were broadly balanced across treatment and dose group with the exception of cough and throat irritation prominently observed after single doses of BI 443651 equal or higher than 1800 µg.

Further details of this study are provided in the Investigator Brochure ([c02337864](#)).

1.2.7 Prediction of human pharmacokinetics

In order to assess expected exposures in a phase I multiple-dose study (1363.2), the preliminary BI 443651 concentration-time data for doses up to 900 µg available were fitted to a single first-order absorption and two-compartment body model for each subject. The modeled data were then used to simulate the planned doses. The predicted exposure data from the preliminary simulations are given in Table 1.2.7:1 below.

2. RATIONALE, OBJECTIVES, AND BENEFIT – RISK ASSESSMENT

2.1 RATIONALE FOR PERFORMING THE TRIAL

This is one of the two first multiple dose administration trials of BI 443651, the other study involving multiple dosing in healthy volunteers, COPD and CF patients. The objective of this study is to investigate the safety and tolerability of BI 443651 in male and female (of non-child bearing potential) subjects with asthma using multiple orally inhaled doses to provide the basis for a potential ongoing clinical development of BI 443651. The study is designed to assess potential drug effects on pulmonary function due to an observed in vitro off target effect of acetylcholinesterase inhibition. Nonclinical assessment in in vivo models demonstrated dose dependent augmentation of pulmonary resistance following acetyl and methacholine challenge ([see Section 1.2](#)).

Patients with asthma have increased airway hyper-responsiveness (AHR) to methacholine, with chronic inflammation and increased AHR leading to symptoms such as shortness of breath by variable expiratory airflow limitation [R97-1015](#). Airway hyper reactivity and narrowing is primarily driven by the bronchial smooth muscle, which is at least partially under the control of the cholinergic system [\[P92-1976\]](#). Asthmatic patients have increased basal airway smooth muscle tone [\[Hashimoto A, 1996\]](#) which may result from increased basal activity of pulmonary parasympathetic cholinergic nerves i.e. increased cholinergic tone, although the degree to which cholinergic tone contributes to airway narrowing in asthmatics is unclear. Proposed mechanisms for the increased cholinergic tone include increased release of acetylcholine from cholinergic nerve endings [P17-01614](#), and reduced levels of neuromodulators that attenuate cholinergic neurotransmission [\[R17-0519, P09-06255\]](#). Inhibition of acetylcholinesterase could alter cholinergic tone by reducing the degradation of acetylcholine, thus leading to bronchoconstriction. The guinea pig ACh/ MCh model represents a sensitive model of cholinergic effects, and although the pre-clinical data suggests there is no safety concern in patients in an unchallenged state, theoretically bronchoconstriction could be observed particularly in patients with heightened cholinergic tone. Patients with asthma should be specifically sensitive to such effects and would represent a population in which to closely monitor for such effects.

This study will derive pulmonary function data following the administration of methacholine in mild asthma subjects after 3 multiple administration of BI 443651 and will act as an early safety study prior to large scale studies in patients with obstructive airways disease. By performing the study in subjects with asthma, safety information can be obtained in subjects with hyper-reactive airways disease to fully explore possible induction of bronchoconstriction that may result due to inhibition of acetylcholinesterase as an off target effect of BI 443651. Administration of methacholine to asthmatics is considered to be the most sensitive method of assessing bronchoconstriction effects of an acetylcholinesterase inhibition in humans and will quantify the effects observed in the non-clinical studies.

In summary this study aims to assess any potential deleterious effects on pulmonary function in man prior to large scale clinical trials.

2.2 TRIAL OBJECTIVES

The primary objective of this study is to investigate safety and tolerability of three consecutive administrations, 12 hours apart, at three different dose-levels (100, 400 and 1200 µg) of BI 443651 administered via oral inhalation in male and female mild asthmatic subjects after a bolus methacholine challenge.

A description of the endpoints to be determined, and the observations along with specific information about how to collect the data, is provided in [Section 5](#).

2.3 BENEFIT - RISK ASSESSMENT

BI 443651 is being developed as a therapy for obstructive airways diseases such as cystic fibrosis and COPD. Participation in this study is without expected (therapeutic) benefit for asthmatic subjects. Their participation in the study is of importance to inform the safety profile of BI 443651 specifically with regard potential adverse effects on lung function prior to progressing to long term clinical studies.

Subjects are exposed to risks related to the study procedures and intake of trial medication as described below.

Procedure-related risks

The use of an indwelling venous catheter for the purpose of blood sampling may be accompanied by mild bruising and also, in rare cases, by transient inflammation of the wall of the vein. In addition, in rare cases a nerve might be injured while inserting the venous catheter, potentially resulting in paresthesia, reduced sensibility, and/or pain for an indefinite period. The same risks apply to venepuncture for blood sampling.

Sampling times and visits may be adapted based on information obtained during trial conduct including addition of samples and visits. The total volume of blood to be withdrawn during the entire study will not exceed 500mL (roughly equivalent to a normal blood donation). No study-related risk to study participants is expected from this blood withdrawal over the course of the study.

Methacholine (MCh) challenge is a routine practice in the diagnosis of asthma in the event of an unclear history or investigations. The main risk is of bronchoconstriction. Pulmonary function will be monitored and adverse findings can be reversed. Adverse effects are expected to be reversible with administration of an inhaled anticholinergic agent (ipratropium bromide) if necessary.

Drug-related risks and safety measures

The nature of the target and the mechanism of action of BI 443651, are well documented. The side effect profile is well understood and the adverse events observed in rats following administration of BI 443651 are consistent with the mechanism.

The animal models are believed to be predictive for the effects in

Proprietary confidential information © 2017 Boehringer Ingelheim International GmbH or one or more of its affiliated companies

humans.

In study 1363.1, 63 healthy male volunteers have been administered single inhaled doses of BI 443651 up to 3600 µg. In this study, BI 443651 was found to be well tolerated (see [Section](#)

he most sensitive species for these effects was the rat with no relevant effects observed in the dog, even at high doses, on serum or urinary electrolytes. No other systemic safety findings were observed in either the toxicology or safety pharmacology studies.

This translates to a safety margin of approximately 11-fold. The urine cover is regarded as the most relevant exposure for safety based mechanism i.e. serum electrolytes.

BI 443651 does not present a genotoxic hazard. BI 443651 is considered to be low risk for phototoxicity, based on its absorbance pattern and lack of toxicity in 4-week repeat dose studies.

Fertility has not been assessed in nonclinical species, but no adverse effects have been observed on reproductive organs in 4-week toxicity studies in rats and dogs, suggesting that there is a low risk to fertility. At the time this current study is planned to start embryo-fetal development studies of BI 443651 will not yet have been conducted.

Off target inhibition of ACh has been observed with augmented effects in non-clinical ACh/MCh challenge guinea pig models. No adverse effects on pulmonary function were observed in the absence of methacholine or acetylcholine challenge. No adverse respiratory effects were detected in the 4-week toxicology studies or in the safety pharmacology studies at doses of up to 7,750 µg/kg in dog or rat. Exaggerated bronchoconstriction effects may be apparent following methacholine challenge however effects on respiratory function will be monitored and are reversible. Inhaled anticholinergic therapy should reverse these effects if required, as is also used if required for MCh testing.

In summary whilst not all safety effects may be predicted, based on mechanism and systemic toxicological finding the only potential systemic toxicity is changes in serum electrolytes and

Proprietary confidential information © 2017 Boehringer Ingelheim International GmbH or one or more of its affiliated companies

particularly increases in serum potassium. Augmented bronchoconstriction may be induced following administration of methacholine. In both cases these changes are easily monitored and treatable if observed. The following safety measures will be applied in this study in order to minimize the risk for the mild asthmatic subjects:

- 1 This study (1363.7) will only start once healthy volunteers have been safely administered 100 and 400 µg b.i.d. of BI 443651 for 7days in a separate ongoing study (1363.2) i.e. no stopping criteria have been triggered in 1363.2.
- 2 Only mild, controlled, stable asthma subjects with well-maintained lung function will be included in the study i.e. subjects on prn SABA or low dose inhaled corticosteroid with an $FEV_1 \geq 70\%$ and no recent respiratory tract infection or exacerbation.
- 3 The study will be split into two parts ([see Section 3.1](#)) with an initial pilot (Part 1) to assess for gross adverse effects of BI 443651 on bronchoconstriction after MCh challenge. In Part 1, subjects will receive BI 443651 in a dose ordered fashion with either placebo **or** the lowest dose first followed by the higher doses and placebo (if not taken first). Individual subjects will not be dosed further if individual stopping criteria (including pulmonary function criteria) are triggered. Stopping criteria are described in detail in [Section 3.3.4](#).

The second part of the study (not necessarily dose ordered) will only proceed if no subjects triggered the first three discontinuation criteria following administration of BI 443651 during Part 1.

- 4 The subjects will be closely monitored throughout the treatment period with frequent evaluation of pulmonary function following MCh challenge. Subjects may only be discharged from clinic after medical assessment has been conducted. The subject's FEV_1 must have returned to $\geq 90\%$ of the first set of spirometry measurements performed that day before the subject can be discharged from the clinic. Rescue medication will be provided as required.
- 5 Safety laboratory testing will be performed during the study with a focus on electrolytes ([see Flow Chart](#)). The study will be stopped if, during Part 1 (pilot) at least 2 subjects in the current cohort or treatment period on active drug showed serum potassium levels $\geq 5.5\text{mmol/L}$ in non-haemolysed blood (confirmed by repeat). In Part 2 (main study), the study would be stopped if 4 subjects on active drug (independent of dose level) showed serum potassium levels $\geq 5.5\text{mmol/L}$ in non-haemolysed blood (confirmed by repeat).

Although rare, a potential for drug-induced liver injury (DILI) is under constant surveillance by sponsors and regulators. Therefore, this trial requires timely detection, evaluation, and follow-up of laboratory alterations in selected liver laboratory parameters to ensure subjects' safety ([see Section 5.3.6.1](#)).

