3. DESCRIPTION OF DESIGN AND TRIAL POPULATION

3.1 OVERALL TRIAL DESIGN AND PLAN

This multiple dose, randomised, placebo controlled, trial will be conducted in two parts. The first part (pilot study) will be a single-blind four-way crossover with dose ordered sequences. The second part (main study) will be a double-blind four-way crossover, conducted according to a William's design. In both parts of the study, BI 443651 or placebo equivalent will be administered three consecutive times, 12 hours apart, per dose level. All subjects will receive placebo, 100, 400 and 1200 µg BI 443651 (in Part 1, the dose groups may be altered in case evolving data suggests a change in dosage is required (see below)). Each period will be separated by a washout period of at least 14 days (and not more than 28 days). Two administrations of BI 443651 will be delivered on Day 1 (morning and evening) and a single administration Day 2 (morning). One hour after dosing on Day 2, MCh challenge will be performed. A methacholine challenge will be conducted on Day -2 to Day -1 for each treatment period, (with the Day -2 to Day -1 challenge providing the baseline for each treatment period) at the same time of the day.

The two parts of the study will be conducted as follows:

Part 1: 4 subjects will be included in the first pilot part of the study each being administered three active doses of BI 443651 and placebo, with the active doses investigated being in ascending order of dose strength. Placebo administered given in a single-blinded manner in any order relative to the active treatment as per Table 3.1:1.

Table 3.1:1 Sequences for pilot part of the study

Treatment Period 1	Treatment Period 2	Treatment Period 3	Treatment Period 4
Placebo	100 µg	400 µg	1200 µg
100 µg	Placebo	400 µg	1200 µg
100 µg	400 µg	Placebo	1200 µg
100 µg	400 µg	1200 µg	Placebo

Part 2: 32 subjects will participate in the trial with each subject being administered three active dose levels of BI 443651 and placebo. This part of the study will be fully randomised, double blind. The decision to proceed to Part 2 will be based upon the safety and tolerability data of Part 1. Part 2 will only be conducted if, in the opinion of the investigator, no safety concerns arose in Part 1 and if none of the pre-specified trial-specific stopping criteria were met ([see Section 3.3.4.2](#)).

Table 3.1:2

Sequences for main part of the study

Treatment Period 1	Treatment Period 2	Treatment Period 3	Treatment Period 4

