Placebo	100 µg	400 µg	1200 µg
100 µg	Placebo	1200 µg	400 µg
400 µg	1200 µg	Placebo	100 µg
1200 µg	400 µg	100 µg	Placebo

The first pilot part of the study will not be started until data from an ongoing multiple rising dose study (1363.2) in healthy volunteers is available from the first two dose groups (100 and 400 µg b.i.d. BI 443651). Only if BI 443651 has been safely administered in study 1363.2 and no stopping criteria have been met, will this study (1363.7) be started.

In Part 1, dose groups will be investigated consecutively in ascending order of doses with a dose escalation review between each treatment period. Data from each treatment level will be reviewed prior to progression to the next treatment level. Only if the previous dose of BI 443651 is safe and well tolerated, without meeting any stopping criteria in subjects administered BI 443651 ([see Section 3.3.4.1](#)), will the subsequent dose be administered ([Table 3.1:1](#)).

In addition a documented Safety Review by the Coordinating Investigator (or an authorised deputy) and appropriate personnel from the Sponsor must take place prior to initiation of Part 2 of the study. Only if BI 443651 is safe and well tolerated in all subjects in the pilot part without the specified number of subjects meeting any individual stopping criteria (see Section 3.3.4.1), will the transition to Part 2 occur.

An unscheduled safety review meeting can be requested anytime for any reasonable cause by the Principal Investigator (or an authorised deputy) or the sponsor of the study, e.g. because of any unforeseen adverse events, etc. Dose escalation or transition to Part 2 will only be permitted if no safety concerns exist in the opinion of the Principal Investigator (or an authorised deputy) and the Trial Clinical Monitor (or an authorised deputy). The minimum data set for review consists of the following data:

- Results from spirometry in all subjects included in the initial pilot part of the study
- AEs in all subjects including in the initial pilot part of the study, up to at least 48h post dosing (including clinically relevant findings from ancillary safety testing listed below) (Note: AEs may be ongoing at the time of Safety Reviews and AE information may be subject to change prior to Database Lock)
- Check of criteria for stopping subject treatment as per Section 3.3.4.1

Proprietary confidential information © 2017 Boehringer Ingelheim International GmbH or one or more of its affiliated companies

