3.3.4 Removal of subject from therapy or assessments

3.3.4.1 Removal of individual subjects

An excessive withdrawal rate can have a severe negative impact on the scientific value of the trial. Every effort should be made to keep subjects in the trial as scheduled. This includes careful subject selection and appropriate explanation of the trial requirements and procedures prior to enrolment as well as an explanation of the consequences of premature withdrawal.

An individual subject is to be withdrawn from trial treatment if:

a	FEV₁ falls ≥ 45% post methacholine challenge from post diluent value If the subject is symptomatic requiring SABA the study physician must be informed and the appropriate assessments taken, regardless of time-point. The PI should be informed of the situation as soon as possible and a decision will then be made by the PI as to whether the subject is to continue to receive MCh challenges at any further visits or be withdrawn.
b	The subject has a confirmed increase in serum potassium of ≥ 5.5 mmol/L in non-haemolysed blood.

Proprietary confidential information © 2017 Boehringer Ingelheim International GmbH or one or more of its affiliated companies

c	The subject shows relevant individual QT prolongation, i.e. a QTcF increase of greater 60 ms from baseline (pre-dose Day 1 of each Treatment Period)) in connection with absolute QT or QTcF greater than 500 ms, which has been confirmed by a repeat ECG recording.
d	The subject has an asthma exacerbation.
e	The subject withdraws consent for trial treatment or trial participation, without the need to justify the decision.
f	The subject needs to take concomitant drugs that interfere with the investigational product or other trial medication
g	The subject can no longer be treated with trial medication for other medical reasons (such as surgery, adverse events, other diseases, or pregnancy)
h	The subject has repeatedly shown to be non-compliant with important trial procedures and, in the opinion of both, the investigator and sponsor representative, is not willing or able to comply with the trial requirements in the future.

If the subject agrees, he/she will undergo the procedures for early treatment discontinuation and follow up as outlined in the [Flow Chart](#) (FC) and [Section 6.2.3](#).

For all subject the reason for withdrawal (e.g. adverse events) must be recorded in the CRF. These data will be included in the trial database and reported.

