3.3.5 Replacement of subjects

A 'completed' subject is defined as a subject who has completed all treatment periods and procedures including MCh challenge. Subjects who do not complete all treatment periods must be replaced. A replacement subject will be assigned a unique study subject number. In part I of the study, the replacement subject will only undergo the treatment periods not completed by the subject he/she replaces. In part II of the study, a replacement subject will be assigned to the same treatment sequence as the subject he/she replaces. The method to include these replacement patients in the analysis will depend on the time point of inclusion of the new patient in the study.

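### The Part 1 replacement rule can make 400 or 1200 µg a pilot subject's first active dose, against the dose-order safety measure, and the potassium stop is binding in Section 2.3 but only proposed in 3.3.4.2

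*Protocol*

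**What the plan says.** **Dose order in Part 1.** Protocol Section 2.3, safety measure 3, states: "In Part 1, subjects will receive BI 443651 in a dose ordered fashion with either placebo" or the lowest dose first, with the higher doses after that. Section 3.1 has each of the four pilot subjects take three active doses and placebo, "with the active doses investigated being in ascending order of dose strength". Table 3.1:1 gives one sequence per subject. Section 3.2 explains that the pilot is there to assess safety before any patient takes the highest dose as the initial one, which it describes as something that Part 2 may allow.

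**Replacement.** Section 3.3.5 states: "Subjects who do not complete all treatment periods must be replaced". It continues: "In part I of the study, the replacement subject will only undergo the treatment periods not completed by the subject he/she replaces". There is no 100 µg lead-in and no exception. In Part 2, by contrast, a replacement is assigned to the predecessor's sequence.

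**Potassium stop.** Section 2.3, safety measure 5, states as definite that the study stops at two subjects (Part 1) or four subjects (Part 2) on active drug with confirmed serum potassium of 5.5 mmol/L or more. Section 3.3.4.2, item 5, gives the same limits under a heading that reserves a right to discontinue. Its footnote calls them proposed thresholds for a potential discontinuation.

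**The concern.** The replacement rule does inside the pilot what the pilot is meant to clear for Part 2: an asthmatic subject can meet 400 or 1200 µg as the first active dose and then have a methacholine challenge. The feared effect is dose-dependent in the animal work. Section 1.2.1 reports enhancement of acetylcholine-induced bronchoconstriction by 51% and 117% at 80 and 160 µg/kg. The human multiple-dose data required before the trial starts are limited: data from study 1363.2 must exist that "is available from the first two dose groups", which are 100 and 400 µg b.i.d. Single doses up to 3600 µg were well tolerated in healthy men, but a reversible drop in FEV1 "and FVC was observed in some volunteers" (Section 1.2.6). A subject's own response at a lower dose is therefore a real protection.

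For potassium, a stopping rule that is binding in one section and discretionary in another leaves the site and sponsor without an agreed action when the count is reached.

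**Working it through.** **Replacement rule**

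Inputs: the four sequences of Table 3.1:1 (P = placebo) and the Section 3.3.5 rule. Let k be the number of periods that the withdrawn subject completed. The replacement then takes periods k+1 to 4. Each cell shows the replacement's first active dose (µg), with its period in brackets.

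| Sequence | k = 1 | k = 2 | k = 3 |
|---|---|---|---|
| 1: P, 100, 400, 1200 | 100 (P2) | 400 (P3) | 1200 (P4) |
| 2: 100, P, 400, 1200 | 400 (P3) | 400 (P3) | 1200 (P4) |
| 3: 100, 400, P, 1200 | 400 (P2) | 1200 (P4) | 1200 (P4) |
| 4: 100, 400, 1200, P | 400 (P2) | 1200 (P3) | none |

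- Totals over 4 × 3 = 12 cases: 100 µg in 1, 400 µg in 5, 1200 µg in 5, none in 1. So 5 + 5 = 10 cases skip 100 µg.
- In 8 of these 10 the high dose is the first treatment of any kind. In the other 2 (sequence 2 with k = 1, sequence 3 with k = 2) placebo comes first, and one or two lower active doses are skipped.
- With k = 0 the replacement takes the whole sequence and no conflict arises. Counting those four cases gives 10 of 16.

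Had another pilot subject been scheduled for that dose in an earlier period? The first scheduled 400 µg is in Period 2 (sequences 3 and 4), and the first 1200 µg is in Period 3 (sequence 4).

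- Yes in 7 of the 10: the three cases with 400 µg in Period 3 and the four with 1200 µg in Period 4.
- No in 3: 400 µg in Period 2 (sequences 3 and 4, k = 1) and 1200 µg in Period 3 (sequence 4, k = 2). In the last case the replacement is, by schedule, the first pilot subject at 1200 µg. The protocol does not say whether the others wait for the replacement.

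Added periods under two possible corrections:

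- Full sequence: k added periods, so 1 to 3 per replacement; the sum over the 12 cases is 4 × (1 + 2 + 3) = 24.
- Skipped active doses only: 1 period in 5 cases, 2 in 5 and 0 in 2; the sum is 5 × 1 + 5 × 2 = 15.

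Each period has two bolus challenges, and each active period has three drug administrations. The full sequence therefore adds 2 to 6 challenges. Adding only skipped doses, where any are skipped, costs 2 to 4 challenges and 3 to 6 active administrations.

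**Potassium stop**

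| | Section 2.3 | Section 3.3.4.2 |
|---|---|---|
| Limit | 5.5 mmol/L, confirmed | same |
| Count, Part 1 / Part 2 | 2 / 4 | same |
| Force | definite stop | proposed threshold, potential stop |

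In Part 1 a single confirmed case on active drug meets individual criterion b. That already blocks escalation (Section 3.1) and the move to Part 2 (Section 2.3). The open question is mainly Part 2: does a fourth case among 32 subjects stop the trial or prompt a review? The documents give no expected rate. If each subject independently had probability p of a confirmed case on active drug, the chance of four or more is 1 − Σ(x = 0 to 3) C(32, x) pˣ(1 − p)³²⁻ˣ. This gives 0.4% at p = 2%, 7.4% at 5% and 40% at 10%. These values of p are assumptions.

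**The case against.** The strongest reply is that the Part 1 safeguard works largely at group level: "In Part 1, dose groups will be investigated consecutively in ascending order of doses with a dose escalation review between each treatment period". A replacement reaches 400 or 1200 µg only after lower levels have been reviewed in other subjects. Part 2 itself starts two of its four sequences at 400 or 1200 µg, so the protocol does not treat a personal lead-in as indispensable. The investigator may also add intermediate doses or stop dosing in Part 1 (Sections 3.1 and 4.1.2). All of this stands, and it limits the harm. It does not remove the conflict: the review gives the replacement no lower first dose, the discretion need not be used, and Part 2 opens only after the pilot has been passed.

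The 12 cases are also not a risk estimate. The problem needs a dropout after Period 1, among four subjects, that does not itself halt escalation, for example: "The subject withdraws consent for trial treatment or trial participation". It could be argued that even this halts escalation, since it is listed in Section 3.3.4.1. However, Section 3.1 ties escalation to the previous dose being safe and well tolerated, and if every dropout halted it the Part 1 replacement rule would have almost no use.

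Two further points are fair. The ascending-order wording of Section 3.1 is not breached by 400 then 1200 µg, so the order conflict lies with Section 2.3; Section 3.1 adds that each subject takes all three active doses. And the reported FEV1 drop is given without dose or arm, so it cannot be attributed to 1200 µg.

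On potassium, the numbers agree, individual withdrawal applies in any case, and every case is reviewed. The gap is one of binding force only.

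**Conclusion.** The concern holds. Section 3.3.5 contradicts safety measure 3 in 10 of the 12 cases where one to three periods were completed, and in 5 of them the first active dose is 1200 µg. In 3 of the 10 there is no earlier scheduled exposure at that dose in another pilot subject. The counts are unweighted and assume that the replacement keeps the predecessor's remaining periods as scheduled in Table 3.1:1. How often this would occur cannot be computed from the documents, and group-level review reduces the consequence. The potassium wording is a second, separate contradiction, with practical effect mainly in Part 2. Both concern subject safety rather than the estimates, and both should be fixed.

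**What to change.** **Section 3.3.5:** require a Part 1 replacement who is to receive any active dose to start at placebo or 100 µg and go up, adding at least the skipped active doses to the missed periods. A replacement who needs only the placebo period adds nothing. Every replacement on active drug then starts at 100 µg. The cost is 0 to 2 added periods per replacement, each with a washout of at least 14 days, and at most 4 added challenges and 6 added active administrations. Restarting the full sequence is simpler to run but costs 1 to 3 periods and 2 to 6 challenges.

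**Sections 2.3 and 3.3.4.2:** use one wording of the potassium stop for both parts. The binding form is preferable, because potassium increase is the main systemic toxicity that Section 2.3 anticipates. Keep the review of single cases. This needs no extra subjects or procedures.
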